3.2 Endpoints

3.2.1 Primary endpoint

The primary endpoint is to evaluate the effect of ensifentrine on the proportion of patients with recovery (Day 29).

- Day of recovery is defined as the first day on which subjects satisfies one of the following two categories from the 7-point ordinal scale:
 - not hospitalized, no limitations of activities;
 - not hospitalized, limitation of activities, home oxygen requirement, or both.

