8.4 Discharge Activities

For the Day of Discharge (Day 29 or the last day in the hospital if discharged before Day 29), the Daily eCRF will be completed as above (**Table 13**) as well as a Discharge eCRF to document how the patient was discharged (**Table 14**).

Table 14. Day of discharge activities.

Assessment	Information
Record discharge information	
 • Discharged (yes/no).* • If discharged, the Date of discharge and reason (e.g., COVID-19 negative, recovered, not discharged [remains hospitalized] etc.) is noted. Date of scheduled follow-up telephone call. • Where the patient was discharged to (e.g., home, rehab center, etc.). • If the patient was COVID-19 positive or negative at discharge (yes/no/unknown). • Which medications the patient was discharged with. • If supplemental oxygen was prescribed for treatment after discharge.

* Patients not discharged from the hospital by Day 29

Some study patients may not be ready for discharge from the hospital by Day 29. In these instances, study treatment and data collection procedures still end on Day 29 (with the exception of contacts in the next section). This information will be noted in the Discharge eCRF as “study treatment complete, but patient remains hospitalized.” This would also be captured in the Day 29 Clinical status assessment (7-point ordinal scale).

Patients that remain hospitalized after Day 29 will be contacted as described in the next section.

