8.5 Post Discharge/Day 29 Contacts

Following Day 29 or discharge from the hospital (if earlier), there will be three points of contact with all study patients, regardless of hospitalization status. Each contact will require the completion of a Follow-up eCRF (**Table 15**).

- Discharge Contact: 4 to 10 days after discharge from hospital, if discharged within the 29-day treatment period.
 - If the patient remains hospitalized after Day 29, study treatment and data collection procedures still end on Day 29 (with the exception of contacts in this section) and contact with the patient will take place 4 to 10 days after receipt of last dose of study medication (Day 29).
- Day 29 Contact: 26 to 32 days after first dose of study medication. If the Discharge Contact and Day 29 Contact fall within same window, this contact will be combined to the Day 29.

- Day 60 Follow-up: 55 to 65 days after first dose of study medication.
 - Should a patient or their medical contact be unable to be contacted at any of these timepoints, a vital records search will be performed to determine the patient’s vital status approximately 60 days after first dose of study medication.

Table 15. Post-discharge follow-up activities.

Assessment	Information
Follow-up date	
 • Date of follow-up contact
Clinical status assessment (7-point ordinal scale)	
 • Assessed and documented, as above for Day 1 (clinical and vital status)
Re-hospitalization status or remains in hospital	
 • Any incidence of re-admission to the hospital following a 24-hour period of discharge (date and duration) that is related to COVID-19 • Date of discharge (if after Day 29) should be noted in the Follow-up eCRF.
Adverse Events assessments	
 • Documented, as above for Day 1

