7 DEFINITIONS

7.1 General

General clinical study definitions are listed in Table 4.

Table 4. Clinical study RPL554-COV-201 general definitions.

able 4. Clinical study RPL554-COV-201 general definitions.		
Term	Definition for Study	
Baseline	The most recent pre-dose assessment prior to first dose of study medication.	
Clinical status assessment	(Protocol Section 8.1.1) Daily clinical status will be assessed using the 7-point ordinal scale adapted from the WHO R&D Blueprint expert group which measures illness severity over time (https://www.who.int/blueprint/priority-diseases/key-	
	action/COVID19 Treatment Trial Design Master Protocol synopsis Final 180 22020.pdf according to the following criteria: 1. not hospitalized, no limitations of activities 2. not hospitalized, limitation of activities, home oxygen requirement, or both 3. hospitalized, not requiring supplemental oxygen but requiring ongoing medical care* 4. hospitalized, requiring any supplemental oxygen* 5. hospitalized, requiring non-invasive ventilation or use of high-flow oxygen devices* 6. hospitalized, receiving invasive mechanical ventilation or extracorporeal membrane oxygenation (ECMO); and	
	7. death	

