Discharge	The patient is discharged and leaves the hospital alive. This does not include if a patient is moved to another unit.
	The time to discharge = the elapsed time (in days) from Day 1 to the earliest day at which the patient is Discharged from hospital (= Day where the 7-point ordinal scale score is equal to 1 or 2).
Improvement in	A decrease from baseline of at least one point in the 7-point ordinal score (eg, 5
clinical status	to 4).
Worsening	An increase from baseline of at least one point in the 7-point ordinal scale score
clinical status	(eg, 5 to 6).

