7.2 Endpoints

Clinical study endpoints and associated definitions are listed in Table 5. Additional definitions are included in Section 8. Analysis tables are included in Section 9.3, Section 9.4 and Section 9.5.

Table 5. Clinical study RPL554-COV-201 endpoint definitions.

Endpoints	•	Definitions
Primary Refer to Section 9,	The proportion of patients who are in recovery state at Day 29.	Clinical status assessed using the 7-point ordinal scale score.
Table 10		The proportion of patients in each treatment arm that meet the definition of recovery.
		Recovery = one of the following two categories from the 7-point ordinal scale: 1. not hospitalized, no limitations of activities; 2. not hospitalized, limitation of activities, home oxygen requirement, or both.
Secondary Refer to Section 9,	Time to a recovery state (Day 1-Day 29; measured in days)	Clinical status assessed using the 7-point ordinal scale score.
Table 11		Time to recovery = elapsed time (in days) from Day 1 to the first day on which patients satisfy either 1 or 2 category listed in the primary endpoint.
	Proportion of patients who are in a recovery state at Days 7, 14 and 60.	Clinical status assessed using the 7-point ordinal scale score.
		The proportion of patients in each treatment arm that meet the definition of recovery.
		Recovery = one of the following two categories from the 7-point ordinal scale:

pg. 14 Confidential

Endpoints		Definitions
		not hospitalized, no limitations of activities; not hospitalized, limitation of activities, home oxygen requirement, or both.
	Proportion of patients with improvement of one category using the 7-point ordinal scale	Clinical status assessed using the 7-point ordinal scale score.
	(Day 1 - Days 7, 14 and 29).	The proportion of patients in each treatment arm that meet the definition of a one category improvement in clinical status.
		Improvement in clinical status = a decrease from baseline of one point in the 7-point ordinal score (eg, 5 to 4).
	Proportion of patients with improvement of two	Clinical status assessed using the 7-point ordinal scale score.
	categories using the 7-point ordinal scale (Day 1 - Days 7, 14 and 29).	The proportion of patients in each treatment arm that meet the definition of a two category improvement in clinical status.
		Improvement in clinical status = a decrease from baseline of two points in the 7-point ordinal score (eg, 5 to 3).

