8.5 Missing Data

All attempts will be made to collect all data per protocol.

 The patients withdrawn from treatment will be followed up regarding their status according to the 7-point ordinal scale at Day 29 as far as possible (exceptions for patients with withdrawn consent or lost to follow-up) and this data will be the primary source for handling missing data in the study.

Any data point that appears to be erroneous or inexplicable based on clinical judgment will be investigated as a possible outlier.

• If data points are identified as outliers, sensitivity analyses may be performed to examine the impact of including or excluding the outliers. Any substantive differences in these analyses will be reported.

For survival analyses, patients with death as outcome will be censored at Day 29 (Day 60), unless the required event was reached prior to death. Patients who are lost to follow-up or terminate the study prior to Day 29 (Day 60) for other reason than death and prior to observing/experiencing the event will be censored at the time of their last observed assessment.

The only time to event analyses is the time to recovery.

For secondary endpoint analyses, the following imputation rules will be used for patients who are lost to follow-up, terminate early from the study, or do not have further outcome data available after discharge for any reason than death:

- Patients with no data collected at the actual time point of interest for other reason than
 death, the last assessment of their status prior to this time point will be used as a
 representative for that time point. Especially, if the patient's clinical status scale is 1 or 2
 at the last observed assessment, then the patient will be considered to be recovered
 through Day 29.
- For endpoints assessing total time (oxygen or non-invasive ventilator care), the status for patients with no data collected for other reason than death, will be assumed unchanged from last assessment of the score up to last day in the definition of the endpoint (Day 29). Thus, no extra days will be added for patients without oxygen or patients without non-invasive ventilator care at last assessment.
- Patients that die in the study will be handled as worst case in all the analyses, that is they are considered to be on oxygen need, non-invasive and invasive mechanical ventilator need for all time points following the death.

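### A live discharge to hospice is scored as recovery, and the plan does not settle how a direct transfer to another hospital is scored

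*SAP*

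**What the plan says.** SAP 7.1 (Table 4) defines discharge as: "The patient is discharged and leaves the hospital alive. This does not include if a patient is moved to another unit". The same row counts time to discharge up to the day of leaving and equates that day with the "Day where the 7-point ordinal scale score is equal to 1 or 2".

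Both of the best categories on the scale presuppose a patient who is out of hospital. The second reads "2. not hospitalized, limitation of activities, home oxygen requirement, or both". Neither names a setting. Scores 3 to 6 all describe hospitalized patients.

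SAP 7.2 (Table 5) defines recovery as score 1 or 2. The primary endpoint is "The proportion of patients who are in recovery state at Day 29". Time to recovery runs to the first day at 1 or 2, with no requirement that the state lasts. Protocol 3.2.1 uses the same idea: "Day of recovery is defined as the first day on which subjects satisfies one of the following two categories".

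Under SAP 8.5, survival analyses censor a death at Day 29 unless the event came first. In the rules listed for secondary endpoints, if there are no later data and the last score was 1 or 2, "then the patient will be considered to be recovered" up to Day 29.

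Discharge destination is recorded (Protocol 8.1, and 8.4 Table 14) but enters no endpoint definition. Neither document mentions hospice or transfer to another hospital. Protocol section 8 asks for comfort care and withdrawal of care to be captured, but only when a patient dies.

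**The concern.** The authors saw that some moves are not true discharges, but they excluded only one kind. A hospice discharge ends the hospital stay because recovery is no longer expected, yet the rule as written places the patient in the best part of the scale. Two patients with nearly the same course are then scored in opposite directions. One who dies in hospital never has a recovery event, while one who goes to hospice and dies soon afterwards has one.

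At stake are time to recovery, Day 7 and Day 14 recovery, and hospital days. With 30 and 15 patients, a single misclassified outcome is visible in the estimates. Those estimates are the useful product of a pilot that SAP 8.2 says may inform on treatment effect for future studies.

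**Working it through.** **Step 1. Follow a patient discharged alive to hospice through each rule.**

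| Endpoint | Rule | Result as written |
|---|---|---|
| Time to recovery (SAP 7.2, 8.5, 9.4.1) | First day at 1 or 2; censoring for death applies only if no event came first | Recovery event on the discharge day; stands after death |
| Recovery at Days 7 and 14 (SAP 7.2, 8.5) | Daily scoring ends at discharge (Protocol 8.1); no contact is fixed at these days; last status is carried forward | Recovered if alive on that day |
| Duration of hospitalization (SAP 7.2) | Days at 3 to 6, plus score 7 if the patient dies while hospitalized | Counting stops at discharge. The worst-case rule for deaths in SAP 8.5 spells out oxygen and ventilation, not hospital days |
| Primary, Day 29 (SAP 7.2) | State at Day 29, re-assessed at the contact 26 to 32 days after first dose | Dead by then: score 7, not recovered. Alive and out of hospital: score 2, recovered |

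The comparison case is a patient who dies in hospital without reaching 1 or 2. That patient is censored at Day 29 in time to recovery and is not recovered at any later time point.

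**Step 2. Follow a patient moved directly to another hospital.** On the discharge definition the patient has left the hospital alive and has not merely changed unit, which points to score 1 or 2. On the scale wording the patient is still hospitalized, which points to scores 3 to 6. Nothing ranks one text above the other. The re-hospitalization item in Protocol 8.5 (Table 15) does not settle it, since it counts "Any incidence of re-admission to the hospital following a 24-hour period of discharge" and a direct transfer has no such interval.

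**Step 3. Size.** The plan states no recovery rate, effect size or power, and no rate of hospice discharge or transfer, so there is no planned figure to reproduce. Arm sizes are 30 and 15 (45 patients at 2:1: 45 × 2/3 = 30, 45 × 1/3 = 15).

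Change in an arm's recovery proportion when k patients are re-scored = k / n.

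- Ensifentrine, one patient: 1/30 = 3.3 points.
- Placebo, one patient: 1/15 = 6.7 points.

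Illustration with **assumed** counts of 28/30 and 13/15 recovered (difference = ensifentrine minus placebo; Fisher's exact test, two-sided, as a simple stand-in for the planned model):

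| Re-scored as not recovered | Ensifentrine | Placebo | Difference (points) | p |
|---|---|---|---|---|
| None | 28/30 | 13/15 | +6.7 | 0.591 |
| One placebo | 28/30 | 12/15 | +13.3 | 0.315 |
| Two placebo | 28/30 | 11/15 | +20.0 | 0.157 |
| One ensifentrine | 27/30 | 13/15 | +3.3 | 1.0 |
| Two ensifentrine | 26/30 | 13/15 | 0.0 | 1.0 |

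Five assumed starting pairs were tried, from 30/30 and 15/15 down to 24/30 and 10/15. Re-scoring one or two patients in a single arm moved the difference by 3.3 to 13.3 points (1/30 to 2/15). The smallest p-value was 0.086, so none fell below 0.05.

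**The case against.** The strongest reply is that recovery is defined from the scale alone, and SAP Table 5 never refers to the discharge definition. The link in Table 4 can be read the other way, with the discharge day derived from the score. On that reading a patient moved to another hospital has not been discharged and stays at 3 to 6. This stands for transfers. A reader might infer that every live departure counts as recovery, but the documents do not say so: for transfers they conflict. It does not rescue hospice, because a patient in hospice outside the hospital is not hospitalized on either reading.

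Second, the primary endpoint is largely protected. The Day 29 contact repeats the scale, the schedule of activities collects still-in-hospital status at each contact, and a vital-records search backs up mortality. This also stands. A reader might infer that carry-forward of recovered status feeds the primary endpoint, but SAP 8.5 lists that rule for secondary endpoints. The protocol's first-day wording leaves open a reading of ever having recovered within 29 days, which would bring hospice discharges into the primary endpoint. The SAP chooses status at Day 29.

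Third, nothing shows that such a discharge occurred. Imminent death was an exclusion, and the SAP shells show all patients as moderate at baseline and 44 of 45 at score 4. The analyses are exploratory. This limits the likely size but does not supply the missing rule.

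Fourth, calling hospice not recovered departs from the literal scale. That is true, and it is a reason to keep the present scoring as a sensitivity analysis.

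**Conclusion.** The point holds for hospice. Followed exactly, the plan counts a live hospice discharge as a recovery event that stands after death. It also counts the patient as recovered at Day 7 or 14 while alive, and it shortens hospital days. The primary endpoint is affected only for a hospice patient alive and not hospitalized at Day 29. For direct transfers the finding is an unresolved conflict between the discharge definition and the scale, so two analysts could score the same patient differently.

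Each affected patient is worth 3.3 points on ensifentrine or 6.7 points on placebo in a recovery proportion. The number of such patients is unknown and may be zero. The direction of any bias depends on the arm in which they fall. On the assumed counts tried, the point estimate moved but nominal significance did not. This should be corrected, but it does not undermine the trial.

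**What to change.** Before unblinding, and using the destination already recorded on the Discharge eCRF:

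1. State in SAP Tables 4 and 5 that a discharge to hospice or comfort care is not a recovery event in time to recovery, and is not recovered at Days 7, 14, 29 or 60.
2. Reconcile the discharge definition with the scale by stating that hospitalized includes any acute-care hospital. A direct transfer then stays at the last known inpatient score until a later contact shows otherwise.
3. Report the primary and time-to-recovery results under the scoring as now written as a sensitivity analysis, with the number of patients re-scored in each arm.

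The cost is a few lines of SAP text and a short code list for an existing field. The recovery proportion may come out slightly lower. Discharge dates from outside facilities may have to come from the follow-up contacts, because Protocol Table 15 asks for a discharge date only when it falls after Day 29.

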7.2 Endpoints

Clinical study endpoints and associated definitions are listed in Table 5. Additional definitions are included in Section 8. Analysis tables are included in Section 9.3, Section 9.4 and Section 9.5.

Table 5. Clinical study RPL554-COV-201 endpoint definitions.

Endpoints	•	Definitions
Primary Refer to Section 9,	The proportion of patients who are in recovery state at Day 29.	Clinical status assessed using the 7-point ordinal scale score.
Table 10		The proportion of patients in each treatment arm that meet the definition of recovery.
		Recovery = one of the following two categories from the 7-point ordinal scale: 1. not hospitalized, no limitations of activities; 2. not hospitalized, limitation of activities, home oxygen requirement, or both.
Secondary Refer to Section 9,	Time to a recovery state (Day 1-Day 29; measured in days)	Clinical status assessed using the 7-point ordinal scale score.
Table 11		Time to recovery = elapsed time (in days) from Day 1 to the first day on which patients satisfy either 1 or 2 category listed in the primary endpoint.
	Proportion of patients who are in a recovery state at Days 7, 14 and 60.	Clinical status assessed using the 7-point ordinal scale score.
		The proportion of patients in each treatment arm that meet the definition of recovery.
		Recovery = one of the following two categories from the 7-point ordinal scale:

pg. 14 Confidential

Endpoints		Definitions
		not hospitalized, no limitations of activities; not hospitalized, limitation of activities, home oxygen requirement, or both.
	Proportion of patients with improvement of one category using the 7-point ordinal scale	Clinical status assessed using the 7-point ordinal scale score.
	(Day 1 - Days 7, 14 and 29).	The proportion of patients in each treatment arm that meet the definition of a one category improvement in clinical status.
		Improvement in clinical status = a decrease from baseline of one point in the 7-point ordinal score (eg, 5 to 4).
	Proportion of patients with improvement of two	Clinical status assessed using the 7-point ordinal scale score.
	categories using the 7-point ordinal scale (Day 1 - Days 7, 14 and 29).	The proportion of patients in each treatment arm that meet the definition of a two category improvement in clinical status.
		Improvement in clinical status = a decrease from baseline of two points in the 7-point ordinal score (eg, 5 to 3).
	All-cause mortality at Days 29 and 60.	Clinical status assessed using the 7-point ordinal scale score.
		Death = 7-point ordinal scale score is equal to 7 or using a vital records search returns a death record, the date on the record will be the date of death.
	Proportion of patients alive and not in respiratory failure (invasive mechanical	Clinical status assessed using the 7-point ordinal scale score.
	ventilation or extracorporeal membrane oxygenation (ECMO)) at Days 7, 14 and 29.	The proportion of patients in each treatment arm that meet the definition of alive and not is respiratory failure.
		Alive and not in respiratory failure (invasive mechanical ventilation or ECMO) = 7-point ordinal scale score is equal to 1, 2, 3, 4 or 5.
	Proportion of patients needing re-hospitalization (post-dose Day 1 – Day 60).	Assessed following discharge: the eCRF question regarding re-hospitalization will be used at Day 29 and Day 60 follow-up contact.
		The proportion of patients in each treatment arm that meet the definition of re-hospitalization following discharge.
		Re-hospitalization = following their treatment with study medication and subsequent discharge from hospital, they were re-admitted to a hospital for COVID related issue(s).

pg. 15 Confidential

Endpoints		Definitions
	Total time of hospitalization	Clinical status assessed using the 7-point
	between Day 1 - Day 29 (measured in days).	ordinal scale score.
	(Hospitalized = # days where the 7-point ordinal scale score is equal to 3, 4, 5 or 6.
		Or 7-point ordinal scale score is equal
		to 7 if patient dies while hospitalized
		between Day 1-29.
	Change from baseline in 7-	Clinical status assessed using the 7-point
	point ordinal scale (Days 7, 14 and 29).	ordinal scale score.
		The mean change from baseline of the 7-point
		ordinal scale in each treatment arm as
	Total time on supplemental	assessed by the statistical analysis. Clinical status assessed using the 7-point
	oxygen (Day 1 - Day 29; measured in days).	ordinal scale score.
	. ,	Hospitalized patient supplemental oxygen = # days where the 7-point ordinal scale score is equal to 4, 5, or 6.
		 Or 7-point ordinal scale score is equal to 7 if patient dies while hospitalized between Day 1-29.
		Not hospitalized patient supplemental oxygen = # days where the 7-point ordinal scale score is equal to 2 (if required to have home oxygen).
	Total time of non-invasive ventilation or high flow oxygen use (post-dose Day 1	Clinical status assessed using the 7-point ordinal scale score.
	- Day 29; measured in days).	Non-invasive ventilation or high flow oxygen use = # days where the 7-point ordinal scale score
		is equal to 5 or 6. • Or 7-point ordinal scale score is equal to 7 if patient dies while hospitalized between Day 1-29.
	Proportion of patients alive and with oxygen use at Days 7, 14 and 29	Clinical status assessed using the 7-point ordinal scale score.
	,	The proportion of patients in each treatment arm that meet the definition of requiring oxygen use.
		Hospitalized patient supplemental oxygen = the 7-point ordinal scale score is equal to 4, 5, or 6. • Or 7-point ordinal scale score is equal
		to 7 if patient dies while hospitalized between Day 1-29.
		Not hospitalized patient supplemental oxygen = the 7-point ordinal scale score is equal to 2 (if required to have home oxygen).
	Proportion of patients alive at Days 7, 14 and 29 with non-	Clinical status assessed using the 7-point ordinal scale score.

pg. 16 Confidential

Endpoints		Definitions
	invasive ventilation or high flow oxygen use	The proportion of patients in each treatment arm that meet the definition of requiring non-invasive ventilation/high-flow oxygen use.
		Non-invasive ventilation or high flow oxygen use = the 7-point ordinal scale score is equal to 5 or 6. • Or 7-point ordinal scale score is equal to 7 if patient dies while hospitalized between Day 1-29.
	Proportion of patients alive and receiving invasive mechanical ventilation or extracorporeal membrane oxygenation (ECMO) at Days 7, 14 and 29).	Clinical status assessed using the 7-point ordinal scale score. The proportion of patients in each treatment arm that meet the definition of requiring invasive mechanical ventilation.
		The 7-point ordinal scale score is equal to 6. • Or 7-point ordinal scale score is equal to 7 if patient dies while hospitalized between Day 1-29.
Safety Refer to Section 9, Table 12	Incidence of Adverse Events (AEs).	Number of AEs and number of patients with AEs for all TEAEs and for subcategories of AEs (SAEs, severe AEs, fatal AEs etc). Incidence = proportion of patients in each treatment arm that experience an adverse
	Adverse Events (AEs) between Day 1 – 29 or discharge and Day 60.	event. Time to combined AE (death, SAE, Severe AE or ET/W from study medication) = elapsed time (in days) from Day 1 to the earliest date of any of the events through hospitalization, Day 29 and Day 60.
	Vital signs during hospitalization between Day 1 – Day 29 or discharge.	 Respiration rate (breaths per minute) Heart rate (beats per minute) Oxygen saturation (SpO2) Supplemental oxygen use (yes/no) Body temperature (Celcius) Blood pressure (mmHg) Level of consciousness graded on the AVPU scale (Alert, Verbal = voice response present, Pain = pain response present, Unresponsive). Other parameters may include (but are not required per protocol): Dehydration status, Fraction of inhaled oxygen (FiO2), Sternal capillary refill time
	Laboratory values during hospitalization between Day 1 – Day 29 or discharge.	

pg. 17 Confidential

